# 1.8 Current vaccination strategy in the Netherlands

Since October 2021, all patients with cancer who received chemotherapy and/or immunotherapy during or within 3 months before their first vaccination received an invitation for a third vaccination with an mRNA vaccine as part of their primary vaccination. This applies to all patients in the VOICE trial who did not receive a third vaccination within the study. Furthermore, everyone is entitled to receive a booster vaccination with an mRNA vaccine at least 3 months after completion of the primary vaccination, whether that consisted

of 2 or 3 vaccinations. This means that the majority of the study participants will have had extra vaccinations at different time points by January 2022. Therefore, we will implement 2 cross sectional measurements at 11 and 18 months after the second vaccination (in February and September 2022) and record the date and type of those extra vaccinations retrospectively. This will provide insight in the immune status against COVID-19 of cancer patients in the Netherlands compared to a cohort without cancer in 2022.

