## Table 1: Flow chart/time and events schedule

Procedure	Screening a	Vacc	Vacc	Day	Day	Day	Vacc	Day	Day	Day	Day
	(within 28	1	2	28	90	180	3 m	28	270	330	540 (±
	days)			vacc	(±7)	(± 7)		vacc	(±7)	(± 14)	21)
				2 b				3			
				(± 3)				(± 3)			
Informed consent	х						х				
Inclusion/exclusion											
criteria	x										
Medical history	х										
Concomitant											
medication	x	х	х	х		X	x	х		x	X
Smoking history	х										
ECOG PS b	х										
Height/weight	х						х				
Vital signs c	х	х	х				х				
Blood tests d		х	х	х		х	х	х		х	х
Nasal MLF				х							
collection e		X									
Sollicited adverse				х							
events f	X	X	X				X				
SAEs g		х	х	х			x				
irAEs h	х	х	х	х			х	х			
AESIs i			Will be	e report	ed for t	he entii	re durat	ion of th	ne study		
Vaccine		~	~								
administration j		X	X				X				
COVID-19					~	~					
questionnaire k	X				X	X	X		x	x	x
Survival status						х				x	x

a Screening should be performed within 28 days prior to the first vaccination but can be done on the same day as the first vaccination.

b ECOG performance status: see appendix 3.

c Vital signs: blood pressure, heart rate, temperature.

d See Table 2.

e MLF = mucosal lining fluid, will be collected using a synthetic absorptive matrix [39] f Participants will complete a questionnaire for solicited systemic and local AEs on a daily basis from each vaccination until 7 days after each vaccination, see Appendix 1. g SAEs that occur within 7 days of each vaccination will be reported

h Newly developed irAEs [38] grade  $\geq$  3 need to be reported for cohort B and D up to 28 days after the second vaccination and from the third vaccination to 28 days thereafter.

i AESIs (see Appendix 2) will be reported by the treating physicians up to 18 months after vaccination for cohorts B-D.

j The name of the vaccine, batch number and date and time of administration will be recorded.

k Participants will complete a questionnaire for diagnosis of SARS-CoV-2 infection, severity and outcome of COVID-19.

 Only participants with an inadequate antibody response (≤300 BAU/mL) on day 28 after the second vaccination.

	Vacc1 a	Vacc2 a	Day	Day		Day		Day

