# 9.2.3 Adverse events of special interest (AESIs)

Adverse events of special interest (AESIs) and serious adverse events (SAEs) frequently occur in patients with cancer who receive systemic therapy as a result of the cancer treatment or the underlying disease. Therefore, AESIs will be collected in this study (see Appendix 2). Treating physicians from patients in cohorts B, C and D will report AESIs to the PI. The coordinating investigator, the PI or delegated trial personnel will report the AESIs through the web portal ToetsingOnline to the accredited METC that approved the protocol, within 15 days after first knowledge of the AESIs.

Since the vaccine is a registered agent, and the number of controls in this study is very small compared to the registration trials, AESIs from the control group will not meaningfully add to the existing safety data. Therefore, subjects in the control group will be asked to report potential side effects of vaccination according to the national guidelines for the general population to the Dutch pharmacovigilance center Lareb.

Death of any cause is considered an AESI, because life expectancy of at least 12 months is required for inclusion. We will report deaths and collect information on cause of death. In order to be as complete as possible, informed consent is asked for coupling of data with the Gemeentelijke Basis Administratie (GBA) and Centraal bureaus voor Statistiek (CBS), also from individuals without cancer. However, this is optional and participants who do not consent to coupling of data with CBS and GBA can participate in the study.

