#### **10.2 Secondary study parameters**

- Incidence and severity of solicited AEs during 7 days after each vaccination is a key secondary endpoint (see Appendix 1). Frequencies and absolute numbers of mild, moderate and severe solicited AEs per cohort will be listed for the first, second and third vaccination separately.
- The numbers, nature and severity of SAEs graded according CTCAEv5.0 will be listed per cohort.
- Incidence and nature of newly occurring irAEs grade ≥ 3 in cohorts B and D up to 28 days after the second vaccination is the second safety endpoint. irAEs will be graded according CTCAEv5.0. Frequencies and absolute numbers of all newly occurring irAEs grade ≥ 3 that occur between the first vaccination and 28 days after the second vaccination in cohorts B and D will be listed.
- Incidence, nature and severity of AESIs comprise the third safety endpoint. AESIs will be graded according CTCAEv5.0. Absolute numbers and frequencies of all AESIs will be listed per cohort and subdivided by severity.
- Levels of SARS-CoV-2 S-specific IgG antibodies at 28 days after the second vaccination will be compared between each patient cohort and the non-cancer cohort using ANOVA or Kruskal–Wallis one-way analysis of variance, and Welch ttests or Mann-Whitney U tests, depending on the distribution of the data.
- Levels of SARS-CoV-2 S-specific IgG antibodies before the second vaccination and at 6, 11 and 18months after the second vaccination will be measured to assess early antibody response and longevity. GMCs and 95% CIs will be calculated. The absolute numbers and percentages of responders will be reported for each cohort for each time point. Antibody levels before the second vaccination and at 6, 11 and 18 months will be compared between each patient cohort and the non-cancer cohort using ANOVA or Kruskal–Wallis one-way analysis of variance, and Welch t-tests or Mann-Whitney U tests, depending on the distribution of the data.

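### AESIs, including deaths from any cause, are listed cumulatively over up to 18 months without time since dose or person-time, which dilutes any excess soon after a dose

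*Combined protocol and SAP*

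**What the plan says.** All references are to the combined protocol and SAP.

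- **Analysis.** Section 10.2 states: "Incidence, nature and severity of AESIs comprise the third safety endpoint". The only tabulation it specifies is: "Absolute numbers and frequencies of all AESIs will be listed per cohort and subdivided by severity".
- **Period and cohorts.** Table 1, footnote i: "AESIs (see Appendix 2) will be reported by the treating physicians up to 18 months after vaccination for cohorts B-D". Section 9.2.3 explains that control participants report side effects to the national pharmacovigilance centre instead, because "AESIs from the control group will not meaningfully add to the existing safety data".
- **Deaths.** Section 9.2.3: "Death of any cause is considered an AESI, because life expectancy of at least 12 months is required for inclusion". It adds: "We will report deaths and collect information on cause of death".
- **Background.** The same section says that AESIs and SAEs "frequently occur in patients with cancer who receive systemic therapy as a result of the cancer treatment or the underlying disease". It gives no rate.
- **Other safety endpoints.** Solicited AEs and SAEs are tied to 7 days after each vaccination (8.1.2). Grade 3 or higher irAEs in cohorts B and D run to 28 days after the second vaccination in 10.2, or after the last one in 8.1.2. Solicited AEs are also listed dose by dose.
- **Dose dates.** Date and time of each study dose are recorded (section 5; Table 1, footnote j). For doses given outside the study, section 1.8 plans to "record the date and type of those extra vaccinations retrospectively", alongside the measurements at 11 and 18 months.
- **A different AESI period.** Section 8.6, on subjects withdrawn from treatment, has AESIs monitored to day 7 in cohorts A and C and to day 28 in cohorts B and D.

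**The concern.** A secondary objective is to assess adverse events after vaccination in patients on immunotherapy, chemotherapy or both. Section 3 expects vaccine-related events mainly in the first week. The AESI listing does not distinguish an event in that week from one a year later, in a population where the plan itself expects frequent events from cancer and its treatment.

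No other part of the plan fills the gap after day 7. SAE and solicited-AE collection has stopped, and irAEs are limited to cohorts B and D. In cohort C, AESIs are then the only systematic adverse-event data. Without AESIs from cohort A there is no concurrent comparison for non-fatal events. Time since dose is then the most direct way to read them, and the plan does not use it.

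Doses outside the study add to the problem. Enrolment ran from February to March 2021, patients were invited for a third dose from October 2021, and section 1.8 expects most participants to have had extra doses by January 2022. These doses fall inside the AESI period. Their dates are gathered afterwards, and may never be obtained for a participant who dies first.

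**Working it through.** The plan states no AESI rate, death rate or detectable excess, so there is no figure of its own to reproduce. The arithmetic below only illustrates how much a cumulative listing dilutes an early excess.

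**Inputs**

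- End of the AESI period: day 540 after the second dose (Table 1).
- Dose interval: 28 days. This is the schedule of the phase III study described in section 1.3 and is assumed to apply here.
- Risk window: 28 days after each dose, borrowed from the irAE endpoint.
- Number of doses: two in the study as a minimum. Three and four are shown because section 1.8 expects extra doses for most participants.
- Further assumptions: constant background rate, complete follow-up, windows that do not overlap.

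**Formulas**

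- Length of the AESI period: T = 28 + 540 = 568 days.
- Share of the period inside the windows with k doses: s = 28k / 568.
- Apparent overall ratio when the rate inside the windows is R times background: (1 − s) + sR = 1 + s(R − 1).

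| Doses | Days in windows | s | Overall ratio, R = 3 | Overall ratio, R = 5 |
|---|---|---|---|---|
| 2 | 56 | 9.9% | 1.20 | 1.39 |
| 3 | 84 | 14.8% | 1.30 | 1.59 |
| 4 | 112 | 19.7% | 1.39 | 1.79 |

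For example, with two doses and R = 5: 1 + 0.099 × 4 = 1.39. With four doses: 1 + 0.197 × 4 = 1.79.

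The result depends on the window. With 7-day windows and two doses, s = 14 / 568 = 2.5%, and a 5-fold excess becomes 1 + 0.025 × 4 = 1.10. Follow-up shorter than 568 days would raise s and reduce the dilution.

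**Deaths.** The documents give no mortality figure. Section 1.6 reports 131 + 229 + 143 = 503 patients evaluable at day 28, a set somewhat smaller than all vaccinated patients. If 18-month mortality were anywhere from 5% to 40% (an assumption), the AESI totals would contain about 503 × 0.05 = 25 to 503 × 0.40 = 201 deaths. That range is too wide to support a statement about size. It shows only why deaths should be tabulated apart from the other AESIs.

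**Passages side by side.** Table 1, footnote i, follows AESIs for 18 months in cohorts B to D. Section 8.6 stops at day 7 or day 28 and includes cohort A. Section 10 puts all vaccinated subjects in the AESI analysis, although 9.2.3 leaves control AESIs outside the study. These statements do not fit together.

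**The case against.** There is a good case on the other side, and it limits the point.

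- Nature of the event is part of the endpoint, cause of death is collected, and section 10 promises individual data points. Guillain-Barré syndrome or anaphylaxis can be read by type, apart from deaths. A reader might infer that cancer deaths swamp any vaccine signal. The documents do not support that: they give no event rates, and events can be told apart by type.
- Study doses are dated as they are given, and the date and type of extra doses are to be recorded too. A reader might infer that no reliable date of the most recent dose exists. That is also unsupported. What stands is narrower: dates of doses outside the study are collected late and may be incomplete, and the AESI listing uses no dose date at all.
- SAEs within 7 days of each vaccination, deaths included, are listed for every cohort. Early serious events after a study dose are therefore captured separately. This leaves the time from day 8 uncovered, and non-serious AESIs at any time.
- Expedited reporting to the ethics committee within 15 days is a separate process from the final tabulation, to which dose dates can still be attached. This is correct, so the reporting deadline is not itself a defect.
- Long AESI collection is a deliberate choice (section 3). The point concerns how the events are tabulated, not how long they are collected.
- An early-versus-late contrast of deaths could mislead. Death is terminal, and entry requires a life expectancy above 12 months, so early mortality may be low by selection. This stands in full and shapes the fix.

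**Conclusion.** The point holds as a gap in the analysis plan that is cheap to close. AESIs alone among the safety endpoints have no anchor to a dose. They are accumulated for up to 18 months, deaths from any cause are included, no person-time is given, and the study collects no AESIs from cohort A. An excess soon after a dose would be diluted. In the illustration, a 5-fold excess within 28 days of two to four doses becomes about 1.4- to 1.8-fold overall.

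Those ratios rest on an assumed 28-day dose interval, a borrowed 28-day window, a constant background rate and full follow-up. They are not figures from the plan, and they do not show any stated figure to be wrong. The safety data are diluted rather than unreadable.

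**What to change.** 1. In 10.2, tabulate non-fatal AESIs by type and by time since the most recent recorded dose of any COVID-19 vaccine (0–7 days, 8–28 days, later), per cohort, with person-time and rates.
2. List deaths separately, by cause and time since last dose. State that this is descriptive and not a within-patient comparison.
3. In 9.2.3, require the AESI report to carry the date and product of the most recent dose, given in the study or outside it. In the tables, flag participants whose extra-dose dates are missing.
4. Reconcile the AESI period in Table 1, footnote i, with that in section 8.6, and state in section 10 which cohorts contribute AESIs.

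**Cost.** Revised wording, one or two extra tables and two fields on the report form, with no added visits or participants. The downside is that sites must look up the last dose date whenever they report an AESI.

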#### 8.1.2 Secondary study parameters/endpoints

- Safety assessment through:
  - Incidence and severity of solicited AEs during 7 days after each vaccination (see Appendix 1)
  - o Incidence and nature of SAEs during 7 days after each vaccination
  - Incidence and nature of newly occurring irAEs [38] grade ≥ 3 in cohort B and D up to 28 days after the last vaccination graded according to the Common Terminology Criteria for Adverse Events version 5.0 (CTCAEv5.0)
  - Incidence, nature and severity of AESIs (see Appendix 2) graded according to CTCAEv5.0
- In depth assessment of immune response through:

- Measurement of SARS-CoV2 specific antibodies before the second vaccination to analyze initial response, and at 6 and 11 and 18 months after the second vaccination to measure longevity
- Measurement of SARS-CoV2 specific antibodies at day 28 after the third vaccination if applicable
- Assessment of SARS-CoV2 specific T cells response at 28 days after the second and third vaccination and at 6, 11 and 18 months after the second vaccination using a high throughput Interferon y ELIspot

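### Antibody levels at 11 and 18 months are analysed as longevity, although the protocol expects most participants to have had further doses by then and no analysis rule uses the recorded doses

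*Combined protocol and SAP*

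**What the plan says.** Section 8.1.2 lists antibody measurement "at 6 and 11 and 18 months after the second vaccination to measure longevity" as a secondary endpoint. Section 10.2 repeats the label: levels before the second dose "and at 6, 11 and 18months after the second vaccination will be measured to assess early antibody response and longevity". It then states the analysis: "Antibody levels before the second vaccination and at 6, 11 and 18 months will be compared between each patient cohort and the non-cancer cohort", by ANOVA or Kruskal–Wallis and Welch or Mann–Whitney tests. Responder percentages are also reported per cohort at each time point. No test includes a term for the number or date of later doses.

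Section 1.8 describes the same visits differently. It expects that "the majority of the study participants will have had extra vaccinations at different time points by January 2022", and for that reason "we will implement 2 cross sectional measurements at 11 and 18 months after the second vaccination". The stated aim is "insight in the immune status against COVID-19 of cancer patients in the Netherlands compared to a cohort without cancer in 2022", and the investigators will "record the date and type of those extra vaccinations retrospectively".

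Section 1.8 also shows that the cohorts were offered different doses. From October 2021, patients treated around the time of their first dose were invited for a third primary dose. Of this invitation it says "This applies to all patients in the VOICE trial who did not receive a third vaccination within the study". The later booster was open to everyone, controls included.

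**The concern.** Durability of the antibody response is a secondary objective (section 2). A level drawn after a third dose or booster does not show how long the response to two doses lasts. It reflects waning, the number and timing of later doses, and any infection in between. The protocol gives this reason itself in section 1.8, yet the endpoint and analysis sections keep the longevity label.

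The comparison with cohort A is exposed as well, because the national programme did not offer patients and controls the same doses. If the cohorts differ at 11 or 18 months, the result could be reported as faster or slower waning when it reflects dose history. A true difference in waning could equally be hidden.

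The T cell and neutralization results carry no longevity label, so the point does not extend to them.

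**Working it through.** The plan states no figure on this point that could be reproduced. The check has four parts.

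**1. Is there a rule for later doses?**

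| Place | What it contains | Uses later doses? |
|---|---|---|
| 8.1.2 and 10.2 | 6, 11 and 18 months all labelled longevity; unadjusted cohort comparisons | No |
| 10, opening text | Excludes baseline seropositives and participants with no dose from immune response analyses | No |
| 10.3, antibody decay | Decay after day 28, with no end point | No |
| 10.3, third-dose items | In-study third dose only | Not national doses |
| 1.8 | Date and type of extra doses to be recorded | Recorded, no analysis attached |

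Section 10 has no exclusion, censoring, stratification or time-since-last-dose rule for later doses. It also has no rule for infection after baseline.

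**2. When do the visits fall?** Inputs: enrolment from 17 February to 12 March 2021 (section 1.6) and the visit windows in Table 1. Assumptions: dose 1 at enrolment, and 28 days between doses, the interval of the phase III study in section 1.3. Dose 2 is then enrolment + 28 days, that is 17 March to 9 April 2021.

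| Visit | Dose 2 + days | With window |
|---|---|---|
| 6 months (180 ± 7) | 13 Sep to 6 Oct 2021 | 6 Sep to 13 Oct 2021 |
| 11 months (330 ± 14) | 10 Feb to 5 Mar 2022 | 27 Jan to 19 Mar 2022 |
| 18 months (540 ± 21) | 8 Sep to 1 Oct 2022 | 18 Aug to 22 Oct 2022 |

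This agrees with February and September 2022 in section 1.8. Table 1 allows screening up to 28 days before dose 1. If dose 1 came 28 days after enrolment, the latest windowed dates move to 10 November 2021, 16 April 2022 and 19 November 2022. The earliest dates do not change.

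So essentially every sample at the two later visits is taken at or after the time by which section 1.8 expects most participants to have had extra doses. The 6-month samples fall mostly before or around the start of the October 2021 invitations.

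**3. How many doses are possible by the later visits?** From section 1.8, a patient can have 3 primary doses + 1 booster = 4. A control can have 2 + 1 = 3, apart from any control given the in-study third dose. These are maxima and say nothing about uptake.

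**4. Does the in-study third dose depend on response?** Yes. It is offered when the day-28 level is inadequate. Numbers evaluable × percentage not adequate (sections 1.6 and 1.7):

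- A: 240 × 0.4% ≈ 1
- B: 131 × 6.9% ≈ 9
- C: 229 × 16.2% ≈ 37
- D: 143 × 11.2% ≈ 16

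For patients this gives (9 + 37 + 16)/(131 + 229 + 143) = 62/503 = 12.3%, against 1/240 in controls. These are participants who could be offered the dose, not those who took it. The count shows only that excluding samples after that dose removes low responders, mostly from the patient cohorts. It does not measure bias.

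**The case against.** The strongest reply is that this is mainly wording. Section 1.8 explains why the later visits exist, calls them cross-sectional and announces a comparison with a cohort without cancer. The per-visit tests in 10.2 carry out that comparison, so none of them need change. The Summary names longevity at 6 months, which suggests the intent, and section 10 promises individual data points. The decay item in 10.3 is only an example and does not commit to using the later samples.

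Much of this stands. The comparison at 11 and 18 months is legitimate as immune status as vaccinated, and the disclosure makes an unqualified durability claim less likely. But section 1.8 is background, the Summary does not say that longevity stops at 6 months, and showing data points does not decide which samples count. The operative sections still direct the analyst to report post-booster levels as longevity.

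Three further limits are accepted. No bias has been demonstrated, since uptake and timing by cohort are not given. Table 1 places the third vaccination after day 180; if that column order is the sequence, few or no 6-month samples would be lost to the in-study dose, and the 62/503 figure matters little there. Infection data are incomplete, so a rule on infection can be applied only in part.

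**Conclusion.** The point holds. Sections 8.1.2 and 10.2 conflict with section 1.8 on what the 11- and 18-month antibody levels measure, and the recorded extra doses enter no analysis. Followed as written, the plan mixes durability with later doses and infections at two of its three longevity time points.

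The size and direction of any effect cannot be derived from the documents. The timing result rests on dose 1 at enrolment and a 28-day interval; delaying dose 1 by up to 28 days does not alter it. The conflict between the sections needs neither assumption. The fault lies in the label and the missing rule, not in the comparison with cohort A. It concerns secondary results only and should be corrected, since durability is a stated objective.

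**What to change.** 1. In 8.1.2 and 10.2, rename the 11- and 18-month antibody results, both levels and responder percentages, as cross-sectional immune status as vaccinated. Keep the unadjusted comparison with cohort A under that name.
2. Limit longevity in 10.2 and decay in 10.3 to samples taken before any vaccination beyond the second and before documented SARS-CoV-2 infection. In practice this is mainly the 6-month sample. Report exclusions per cohort by reason (in-study third dose, national third dose, booster, infection). State that exclusion for the in-study dose is informative, because a low day-28 response triggers it.
3. Describe the 11- and 18-month antibody results by number of doses and time since the last dose. Keep this descriptive, because both are post-baseline variables. Matching tables for T cell and neutralization results are optional.

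The cost is wording in three sections and some tables, since the date and type of extra doses are already to be recorded. The price in content is that the longevity conclusion rests mainly on 6 months. Dose-history groups may be small and overlap poorly between patients and controls. Infection status depends on questionnaires, with RIVM test results only for those who give separate consent.

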# 2. OBJECTIVES

Primary Objective:

 To assess the antibody based immune response after vaccination against COVID-19 in patients with cancer treated with immunotherapy and/or chemotherapy as compared to controls

Secondary Objectives:

- To assess adverse events (AEs) after vaccination against COVID-19 in patients with cancer treated with immunotherapy and/or chemotherapy
- To assess durability of the antibody response in patients with cancer treated with immunotherapy and/or chemotherapy
- To analyze the SARS-CoV-2 specific T cell response after vaccination in patients with cancer treated with immunotherapy and/or chemotherapy

Exploratory Objectives:

- To perform in-depth analysis of cellular immune responses in patients with cancer treated with immunotherapy and/or chemotherapy
- To identify baseline (immune) parameters associated with vaccination response in patients with cancer treated with immunotherapy and/or chemotherapy
- To assess the neutralizing capacity of antibodies against SARS-CoV-2 after vaccination in patients with cancer treated with immunotherapy and/or chemotherapy
- To analyze induction of mucosal antibodies against SARS-CoV-2 in mucosal lining fluid samples. To describe the incidence of SARS-CoV-2 infection, outcome of COVID-19 during 12 months after vaccination in patients with cancer treated with immunotherapy and/or chemotherapy
- To analyze SARS-CoV-2-binding antibody concentration after a third vaccination in participants without an adequate antibody response after two vaccinations
- To analyze safety of a third vaccination

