#### 3. STUDY DESIGN

This is a prospective multicenter cohort study, designed to evaluate the immune response and safety after vaccination against COVID-19 in three cohorts with cancer patients and one cohort of participants without cancer (see Fig.1). The patient cohorts are defined by type of cancer treatment. Immunotherapy, chemotherapy and chemo-immunotherapy were chosen because these treatment regimens may affect the efficacy and safety of vaccination against COVID-19 in different ways.

Figure 1. Trial design

To reflect the real-world population of patients with cancer treated with immunotherapy and/or chemotherapy, this trial is designed as inclusive as possible. Exclusion criteria are minimal and serve to exclude patients who are not evaluable, or in whom vaccination is considered not safe or not effective. A cohort of volunteers without a cancer diagnosis is included for comparison. Because age is an important predictor of the ability to mount an effective immune response to vaccination [37], partners of patients are enrolled in cohort A. We will take care that from all patient cohorts partners are approached, until cohort A is complete. We anticipate that accrual of cohort A will be completed earlier than the patient cohorts.

All participants will receive two vaccinations against COVID-19 according to standard of care. Participants with an inadequate antibody response will be offered a third vaccination. To assess immune responses after vaccination, blood samples will be collected at baseline (i.e. prior to first vaccination), at the day of the second (and if applicable the third) vaccination and at day 28 after the second and third vaccination and 6, 11 and 18 months after the second vaccination by venipuncture. To evaluate hematology, with or without liver and kidney function, additional blood samples will be collected at baseline, at the day of the second and third vaccination, and at day 28 after the second and third vaccination and 6, 11 and 18 months after the second vaccination. Nasal mucosal lining fluid will be collected at baseline and at day 28 after the second vaccination according to a non-invasive sampling method.

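### Antibody and T cell levels are compared between non-randomised cohorts without adjustment for age or sex, and the 11- and 18-month levels are labelled longevity although extra doses, which differ by cohort, enter no comparison

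*Combined protocol and SAP*

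**What the plan says.** **Comparisons.** Section 10.2 says of the levels outside day 28: "Antibody levels before the second vaccination and at 6, 11 and 18 months will be compared between each patient cohort" and the cohort without cancer. The tests are ANOVA or Kruskal–Wallis, then Welch t or Mann–Whitney, chosen by distribution. Day-28 antibody levels and T cell counts are treated the same way. Section 10 names no covariate, matching or stratification for any comparison. Gender appears only as a descriptive subgroup, and section 10.3 relates baseline parameters to response univariately.

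**Age.** Section 3 gives the reason for using partners as controls: "Because age is an important predictor of the ability to mount an effective immune response to vaccination". Partners are to be approached from all patient cohorts until cohort A is full.

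**Purpose of the late samples.**
- Section 2, secondary objective: "To assess durability of the antibody response in patients with cancer treated with immunotherapy and/or chemotherapy".
- Section 8.1.2: antibodies measured "at 6 and 11 and 18 months after the second vaccination to measure longevity".
- Section 10.2: levels before dose 2 and at 6, 11 and 18 months "will be measured to assess early antibody response and longevity".
- Summary: the secondary endpoint is longevity at 6 months only.
- Section 1.8: "we will implement 2 cross sectional measurements at 11 and 18 months after the second vaccination", to give "insight in the immune status against COVID-19 of cancer patients in the Netherlands compared to a cohort without cancer in 2022".

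**Extra doses.** Section 1.8 expects most participants to have had extra vaccinations by January 2022 and will "record the date and type of those extra vaccinations retrospectively". Neither item enters an analysis in sections 10.1 to 10.3.

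**The concern.** There are two separate problems.

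First, cohorts B, C and D are defined by treatment and each is compared with one pooled control group. If age or sex differs between a patient cohort and cohort A, the unadjusted test attributes that difference to cancer or its treatment. The protocol accepts that age matters and then relies on recruitment alone to deal with it.

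Second, by the 11- and 18-month samples the measured level reflects two study doses plus whatever came later. A difference from controls, or its absence, could be reported as durability of the two-dose response when it also reflects third doses, boosters or infection. Access to those doses differs by cohort, and in-study third doses went to people selected for a low day-28 level.

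**Working it through.** The plan states no figure on this point, so the check sets the sections side by side and then asks how sensitive the comparisons are.

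**1. Sensitivity to imbalance.** Section 1.6 gives the evaluable numbers for the day-28 antibody endpoint: A 240, B 131, C 229, D 143. In SD units, SE = √(1/240 + 1/n).
- B: √(1/240 + 1/131) = 0.1086
- C: √(1/240 + 1/229) = 0.0924
- D: √(1/240 + 1/143) = 0.1056

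If confounding shifts the mean by d standard errors, the two-sided false-positive rate is P(|Z + d| > 1.96). This is 10% at d = 0.652 and 20% at d = 1.115. Multiplying by the SE gives:

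| Cohort vs A | Shift for 10% | Shift for 20% |
|---|---|---|
| B | 0.071 SD | 0.121 SD |
| C | 0.060 SD | 0.103 SD |
| D | 0.069 SD | 0.118 SD |

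With 20% fewer samples the ranges are 0.067–0.079 and 0.115–0.135 SD. As an illustration on assumed values (0.1–0.2 SD per decade of age, a 5-year gap in mean age), the shift is 0.5 × 0.1–0.2 = 0.05–0.10 SD and the rate is 7.5% to 19.1%. These figures show sensitivity, not bias. The counts are for antibodies; the protocol does not show that they apply to T cells.

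**2. Which samples are exposed to extra doses.** Assume the first dose fell on the enrolment day (17 February to 12 March 2021, section 1.6) and doses were 28 days apart, as in the phase III study described in section 1.3. Then:
- dose 2: 17 March to 9 April 2021
- day 180: 13 September to 6 October 2021
- day 330: 10 February to 5 March 2022
- day 540: 8 September to 1 October 2022

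The last two agree with the February and September 2022 dates in section 1.8. Screening up to 28 days before dose 1 could move all dates up to 28 days later. National third-dose invitations began in October 2021, and Table 1 places the in-study third dose after day 180. So the 6-month samples fall mostly before, or around, the start of extra dosing, and the 11- and 18-month samples fall after it.

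**3. Who could get extra doses.**
- National third primary dose: patients who had not had one in the study.
- Booster: everyone, at least 3 months after a primary series of two or three doses.
- In-study third dose: participants at or below 300 BAU/mL on day 28 (notes to Tables 1 and 2). From section 1.6 the shares without an adequate response give:
  - B: 6.9% × 131 ≈ 9
  - C: 16.2% × 229 ≈ 37
  - D: 11.2% × 143 ≈ 16
  - A: 0.4% × 240 ≈ 1

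That is about 62 of 503 patients (12%) against about 1 of 240 controls. These are eligible numbers; uptake is not given.

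**4. What a dosing difference could do.** If an extra dose multiplies concentration by f in everyone, and the shares who had one differ by Δ, the spurious GMC ratio is f^Δ. The protocol gives neither f nor Δ. On assumed values:
- 2-fold, 10 points: 2^0.1 = 1.07
- 5-fold, 20 points: 5^0.2 = 1.38
- 10-fold, 30 points: 10^0.3 = 2.00
- 20-fold, 50 points: 20^0.5 = 4.47

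The ratio favours whichever cohort had more extra doses.

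**The case against.** Much of the defence stands. Partner controls address age by design, from all patient cohorts. The primary test is not involved. At day 28 the reported gap in adequate response (99.6% in A against 83.8% to 93.1%) is large, so adjustment there would more likely change its size than its direction. The durability objective concerns patients and does not itself ask for a comparison with controls, and it has a 6-month time point that is largely clean. Section 10 also promises assumption checks, scripts and individual data points. None of this puts age, sex or later doses into a comparison.

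Some stronger readings are tempting but not supported:
- **Age imbalance shown by numbers.** With 240 controls and 503 patients, at least 263 patients (52%) have no partner in the evaluable control group. A reader might infer imbalance, but partners of the other 48% could have the same age distribution as all the patients.
- **Time since last dose derivable from section 1.8.** Invitations ran from October 2021 without a stated end, boosters could follow two doses or three, in-study third doses add another schedule, and day 330 has a window of ±14 days. No complete range follows.
- **Decay analysis already compromised.** Section 10.3 names decay after day 28 as an example, with no end time. It is affected only if it runs past the first extra dose.
- **Adjusting for dose history recovers two-dose durability.** It does not. Extra doses come after baseline and depend on cohort and, for in-study doses, on the earlier antibody level.

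**Conclusion.** The concern holds for secondary and exploratory analyses. The level comparisons are unadjusted although the protocol names age as a predictor and sets no rule on sex. No actual bias has been shown: without age or sex data by cohort, neither its size nor its direction can be derived. A shift of 0.06 to 0.07 SD would be enough to double the nominal error rate.

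The 11- and 18-month between-cohort comparison can answer the section 1.8 question about immune status in 2022. It cannot be read as durability of the two-dose response, and the Summary and sections 1.8, 8.1.2 and 10.2 do not agree on which it is. How far extra doses distort it is also unknown, since uptake and timing by cohort are not given. The finding that 6-month samples are largely unaffected rests on the dating assumptions in the working.

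**What to change.** 1. **Adjustment.** Keep the listed tests. Add to section 10.2 a supplementary linear model of log10 antibody concentration on cohort, age and sex, reporting adjusted GMC ratios against cohort A with 95% CIs. Add an age- and sex-adjusted analysis of T cell counts, rank-based or ordinal if needed. Label these post hoc for day 28 and for any other time point already analysed. Leave the primary test as it is.
2. **Late samples.** Reconcile the Summary with sections 1.8, 8.1.2 and 10.2. State that the 11- and 18-month between-cohort comparison describes immune status in 2022 whatever the extra doses. Report it with a breakdown by number of extra doses (in-study and national) and time since the last one. Base two-dose durability on samples taken before any extra dose or recorded SARS-CoV-2 infection, mainly at 6 months, and apply the same cut to antibody decay in section 10.3.
3. **Limits to state.** Few samples free of extra doses will remain at 11 and 18 months, and they will be selected, because extra doses depend on cohort and, for in-study doses, on the day-28 level. Adjustment cannot separate cancer from its treatment, because cohort A has no cancer.

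The cost is SAP wording and a few models. Gender, the dates and types of extra vaccinations, and infections are already to be recorded, and age is needed for eligibility. No participants or samples are added.
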